### 9.2.1. Source population

The source population consists of all subjects that are registered for at least one year with one of the participating databases during the study period.

### 9.2.2. Study Period

The study period will start on January 1st 2004 (year of licensing) for all databases except January 1st 2006 for SIDIAP (as data is only available from 2005, and a 1-year washout is required) and will end at the most recent version of data that is available with each of the database custodians.

The study period will be divided into three analysis periods for the assessment of RMM effectiveness: up to May 2013 (*reference* period before first DHPC and revised SmPC), between June 2013 and March 2014 (*transitional* period), and after April 2014 (*assessment* period after second DHPC and new SmPC revision).

As for the safety studies, the study period will be divided in two analysis periods: 1. up to May 2013 (when the first DHPC was published, imposing new contraindications), and 2. from June 2013 (when patients with any of the new contraindications should not be prescribed SR any longer) onwards.

### 9.2.3. Study population

The study population for this study comprises:

1. The source population for the measurement of RMM effectiveness.
2. New (not using drug in year prior to cohort entry) strontium ranelate users and new oral bisphosphonates users (BP) for the safety study.

### 9.2.4. Inclusion criteria

#### Effectiveness of RMM

Patients may enter the study cohort when they meet the following inclusion criteria:

1. Continuous enrolment in the database for at least 1 year prior to the start of follow-up.

#### Safety

1. Continuous enrolment in the database for at least 1 year prior to the start of follow-up.
2. 50 years or older upon cohort entry (prescription for new SR or oral BP). The chosen cut-off for an age restriction (50 years) is based on a standard age for menopause and related disorders including post-menopausal osteoporosis, which will avoid or minimize the inclusion of users of anti-osteoporosis medications for reasons other than fracture prevention such as Paget's disease of bone.
3. Incident use of strontium ranelate (no use in year prior to cohort entry) or incident use of oral bisphosphonates (alendronic, risedronic, and ibandronic acid) during follow-up.

The list of ATC/BNF codes used for the identification of patients is detailed in Appendix 14.3.1.

### 9.2.5. Exclusion criteria

#### 9.2.5.1. Effectiveness of RMM

None.

### 9.2.5.2. Incidence rates of safety endpoints

None.

### 9.2.5.3. Comparative safety study

Patients with any of the newly defined contra-indications will be excluded:

1. Established, current or past history of ischemic heart disease (IHD),
2. Peripheral arterial disease (PAD),
3. Cerebrovascular disease (CVD),
4. Uncontrolled hypertension, defined by MAH using an operational definition as follows: a patient will be defined as 'uncontrolled hypertension' if the 3 following conditions apply:
  - a. There is a previous diagnosis of hypertension coded in electronic medical records.
  - b. There is documented use of any anti-hypertensive therapy (either at that time or in the previous year before SR/BP initiation).
  - c. There are at least two readings of Systolic Blood Pressure  $\geq 150$  or Diastolic Blood Pressure  $\geq 95$  mmHg recorded in the 3 months prior to SR/BP initiation.

Also, eligible patients with a diagnosis of Paget's disease of bones will be excluded. And for the outcome VTE we will exclude patients with a previous VTE.

### 9.2.6. Follow-up

#### 9.2.6.1. Effectiveness of risk minimization

Patients will be followed from the latest of the following dates:

- Start of study period.
- One year of valid data in database.

Until the earliest date of:

- The end of enrolment in the database (due to moving out or death).
- Date of last data capturing in the database.

These analyses will be performed in three periods (*reference, transitional, and assessment periods as defined above*) based on the date of cohort entry.

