#### 9.2.6.2. Safety study

Patients will be followed from the date of incident prescription of strontium ranelate or oral bisphosphonate (after one year of non-use) which follows the latest of the following dates:

- Start of study period.
- One year of valid data in database.

Until the earliest date of:

- The end of enrolment in the database (due to moving out or death).
- Date of last data capturing in the database.

The safety study will be performed in two periods (up till May 2013 and from June 2013 onwards) based on the date of cohort entry.

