#### ***Contra-indications***

Prevalence of each of the contraindications will be estimated on a patient level (new and prevalent users of SR) by age, sex, period and country. 95% Confidence Intervals will be estimated using a binomial distribution.

Interrupted time series analyses will be carried out to assess the impact of the RMM on these. Each contributing data source will be analyzed using an interrupted times series design (Kastner, 2011), using repeated measures before (up until May 2013) and after intervention (from April 2014 onwards), using a *transitional* lag time period (from June 2013 to March 2014, both included) to control for secular trends. Using this design, each database acts as its own control.

Using the interrupted times series approach, we estimate the trend in the prevalence rates in monthly intervals during the study period in the three analysis periods, and test for changes pre- and post- intervention, using the *transitional* period as a pre-specified lag time for the intervention to take effect on a) the overall (absolute rate) of outcome, and b) the slope of the trend in rates of outcome.

Segmented linear regression models will be used to estimate the monthly proportions of outcomes. Controlling for baseline level and trend, the models estimate changes in levels and trends of rates after the pre-defined interventions. The regression model includes terms to estimate the pre-existing level for each rate in the first months of the observation period (intercept), trend in the rate before the interventions were introduced, change in level of the rate during the transitional/lag time period, and change in trend after the intervention (Serumaga, 2011).

These analyses will be conducted separately for prevalent and incident SR users.

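### Section 9.2.6.1 assigns the RMM analysis periods by date of cohort entry, which in that cohort is unrelated to strontium ranelate use and contradicts the calendar-time rules elsewhere in the protocol

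*Protocol*

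**What the plan says.** Section 9.2.6.1 states that the three RMM periods are allocated "based on the date of cohort entry". What cohort entry means in this study follows from four places:

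- Section 9.2.3 gives the study population as "The source population for the measurement of RMM effectiveness".
- Section 9.2.1 defines that population as "all subjects that are registered for at least one year with one of the participating databases during the study period".
- Section 9.2.4 sets one inclusion criterion: "Continuous enrolment in the database for at least 1 year prior to the start of follow-up". Section 9.2.5.1 lists no exclusions.
- Section 9.2.6.1 introduces the start of follow-up with "Patients will be followed from the latest of the following dates" and lists two dates, the start of the study period and one year of valid data. On the first, section 9.2.2 says "The study period will start on January 1st 2004 (year of licensing) for all databases", with 2006 for SIDIAP.

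Section 9.2.6.2 uses the same allocation phrase for the safety study. There the anchor is different: "Patients will be followed from the date of incident prescription of strontium ranelate or oral bisphosphonate".

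The RMM analysis in section 9.7.2.2 is described on another time axis: "we estimate the trend in the prevalence rates in monthly intervals during the study period in the three analysis periods".

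**The concern.** In the safety study the date of cohort entry is the date treatment starts, so allocating periods by it is sensible. In the RMM study it is the date a person becomes observable in the database. Someone registered long before the first DHPC keeps a reference-period entry date permanently, whenever SR is prescribed. Only people whose first valid year is completed in April 2014 or later can carry the assessment label.

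The three RMM objectives in section 8 ask for utilisation, contraindications and fulfilment of the new indications in each period. Under the literal rule, the reference estimates would absorb prescribing that took place after both DHPCs. The assessment estimates would describe only recent registrants. Period-specific figures produced that way would not show what happened before and after the measures.

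**Working it through.** **Plan's own figure.** The protocol gives no figure for period allocation. The nearest RMM figures are the precision sizes in section 9.5.1, which reproduce from n = 1.96² × p(1 − p) / 0.05²:

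- p = 0.295: 319.6, so 320.
- p = 0.192: 238.4, so 239.
- p = 0.531: 382.7, so 383.

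They do not depend on the allocation rule and are unaffected by this point.

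**What the rule does to one patient.** Take a database other than SIDIAP, registration from before January 2003 and a first SR prescription in June 2014. Entry is 1 January 2004, so the label is reference. In general:

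- One valid year completed by 31 May 2013 (registration by about end May 2012) gives reference.
- One valid year completed from 1 April 2014 (registration from about April 2013) gives assessment.
- Anything between gives transitional.

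**Where the rest of the protocol places SR use.**

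| Section | Time anchor |
|---|---|
| 9.2.2 | The study period itself is divided by calendar date |
| 8, RMM objectives | SR users within each of the three periods |
| 9.7.2.1, population level | New and prevalent users counted by calendar month; a new user has 365 days without SR before the index prescription |
| 9.7.2.1, patient level | Prevalent users identified at their first prescription within the analysis period |
| 9.7.2.2 | Monthly series up to May 2013 and from April 2014, with the months between as lag |
| 9.2.6.1 | Date of entry to the source-population cohort |

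The last row disagrees with all the others. One fixed label per patient cannot generate the outputs in the rows above it.

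**How many users would be mislabelled (illustration).** The protocol gives no joining rates. Assume that time since cohort entry among SR users is exponential with mean m years, and that SR use is spread evenly from 1 April 2014 to the data cut. Measure t in years from 31 May 2013. Then a = 10/12 at 1 April 2014, T is the data cut and L = T − a.

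- Share labelled reference = m (e^(−a/m) − e^(−T/m)) / L
- Share labelled assessment = 1 − m (1 − e^(−L/m)) / L

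The only turnover-type figure in the protocol is THIN's average follow-up of 5.5 years (section 9.4.3), used here purely as an assumption. For m = 5.5 and data to end 2016, T = 3.583 and L = 2.75. The reference share is 5.5 × (0.859 − 0.521) / 2.75 = 68%.

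| m (years) | Reference, data to end 2014 / 2015 / 2016 | Assessment, data to end 2014 / 2015 / 2016 |
|---|---|---|
| 2 | 55% / 44% / 36% | 17% / 33% / 46% |
| 3 | 67% / 57% / 50% | 12% / 24% / 35% |
| 5.5 | 80% / 74% / 68% | 7% / 14% / 21% |
| 8 | 86% / 81% / 76% | 5% / 10% / 15% |
| 12 | 90% / 87% / 83% | 3% / 7% / 11% |

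The remainder in each case is labelled transitional. These are averages over the interval from April 2014 to the cut. For users on the single date of end December 2016 with m = 5.5, the assessment share is 1 − e^(−2.75/5.5) = 39% and the reference share is e^(−3.583/5.5) = 52%.

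**The case against.** The strongest reply is that nobody following section 9.7.2 could apply the literal rule without noticing. That section counts users by month, anchors prevalent users on a prescription inside the period, and fits the interrupted time series on calendar months. A later statistical analysis plan could settle the matter. This stands, and it makes the harm conditional. A reader might infer that the before/after contrast is lost altogether. The document does not support that: the effectiveness test is the monthly series, and its time axis is correctly stated.

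It can also be said that section 9.2.6.1 never defines cohort entry for the RMM study, and that the only explicit gloss, under the safety inclusion criteria in section 9.2.4, ties it to the prescription. Equating RMM entry with the start of follow-up is an inference, but sections 9.2.1, 9.2.3 and 9.2.4 leave little room for another. Reading it as the first SR prescription would not rescue the sentence either. A patient who started in 2010 and still used SR in 2014 would stay in reference, although section 9.7.2.1 makes that patient a prevalent user in the assessment period. Prevalent users are the larger group (27,764 against 5,819 incident in 2012, Table (9.5) 1).

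Finally, the size cannot be pinned down from the document. That also stands. A reader might want a firm bound on the misallocated share, but none is available, because the result moves with the assumed turnover and the data cut.

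**Conclusion.** Wrong as written. The allocation sentence in section 9.2.6.1 uses a date that has nothing to do with SR use, and it contradicts sections 9.2.2 and 9.7.2. If followed, it would distort the period-specific estimates that the three RMM objectives call for. Under an exponential model with mean time since entry of 3 to 12 years, about 50% to 90% of SR users from April 2014 onwards would be labelled reference, depending on the data cut. With a mean of 2 years the range is 36% to 55%. These percentages rest on assumed turnover, on even use over time and on a stable population. The document supplies none of these, and the THIN figure covers one database only. It is therefore safe to say that many users would be mislabelled. That most would be is plausible but not established. The interrupted time series is not itself misdefined.

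**What to change.** Replace the allocation sentence in section 9.2.6.1 with allocation by calendar date of SR use, in line with section 9.7.2:

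- **Incident users:** by the date of the index SR prescription, meaning one preceded by 365 days without SR. Index is the safer word here. A patient who restarts in 2014 after a year or more off treatment counts as a new user under section 9.7.2.1, and a rule based on the first-ever prescription could return that patient to the reference period.
- **Prevalent users:** by their first prescription within each analysis period for the period-level estimates, and by calendar month of SR use for the monthly series.
- State that one patient may contribute to more than one period.

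Keep allocation by cohort entry in section 9.2.6.2, where entry is the incident prescription.

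The cost is a short replacement text. It needs no additional data, and the precision sizes in section 9.5.1 do not change. It is best made before the common extraction script (section 9.6.5) is written, because a literal implementation there would carry through to all five databases.

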#### 9.2.6.2. Safety study

Patients will be followed from the date of incident prescription of strontium ranelate or oral bisphosphonate (after one year of non-use) which follows the latest of the following dates:

- Start of study period.
- One year of valid data in database.

Until the earliest date of:

- The end of enrolment in the database (due to moving out or death).
- Date of last data capturing in the database.

The safety study will be performed in two periods (up till May 2013 and from June 2013 onwards) based on the date of cohort entry.

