## 6. MILESTONES

Milestone	Planned date
Protocol submission to EMA	by 30 June 2014
Protocol approval by EMA	March 2015 *
Contract signature for study roll-out phase	April 2015*
Registration in the EU PAS register	April 2015*
Start of data collection	April 2015*
Statistical Analysis Plan	May 2015
End of data collection	End of June 2015
PSUR Update 1	October 2015
Start of data collection (second wave)	April 2016
End of data collection (second wave)	End of June 2016
PSUR Update 2	October 2016
Start of data collection (third wave)	April 2017
End of data collection (third wave)	End of June 2017
PSUR Update 3	October 2017
Final report of study results	End of November 2017

*\*Delay will impact the subsequent dates*

Milestones have been planned to maximise the efficiency and availability of data retrieval from the different data sources. A summary of such information is provided here:

Data source (Country)	Periodicity of updates	Time of the year when updates are released	Data availability for each update
SIDIAP (Spain)	Yearly	April-May	End (December 31 st ) of previous calendar year
IPCI (NL)	Yearly (twice is possible)	April-May	Variable as GPs provide not all at same time
THIN (UK)	Three times per year	Irregular	Variable as GPs provide not all at same time
HSD (Italy)	Every 6 months	June and December	End of previous calendar year (in June); up to June in December.
AUH (Denmark)	Yearly	May	December 31st the previous year

Both national regulations and prescribing practices have changed throughout the participating databases in recent months. As a consequence, in Italy, where GPs in primary care are not allowed anymore to initiate or renew strontium ranelate treatment since December 2013, the number of incident strontium ranelate users in the assessment period is expected to be null or very low. This point will be assessed for the first PSUR update (October 2015) as part of the analyses of the utilization patterns at population level (see [section 9.7.2.1](#)).

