### 9.3. Variables

#### 9.3.1. Safety endpoints

**Ascertainment of cases:** cases will be all persons with a first occurrence after cohort entry of:

- Acute myocardial infarction.
- Thromboembolic events (deep venous thrombosis and pulmonary embolism).
- Cardiovascular death.

Cases will be identified from the medical records (see codes in Appendix 14.3).

Acute myocardial infarction has been recently validated in all of the participating data sources (Coloma, 2013; Ramos, 2012) and will therefore not need further linkage or validation studies.

Thromboembolic events have been validated in the UK CPRD/THIN (Lawrenson, 2000) and Aarhus (Severinsen, 2010), and these previously validated algorithms will be used to identify cases. A random sample of cases of thromboembolic events in each data source will be validated using either free text manual review (IPCI, HSD, and Aarhus) or linkage to hospital admissions data (THIN and SIDIAP). If the estimated positive predictive value in these samples is >75%, no further validation will be performed for thromboembolic events. Otherwise, all the events observed in the safety study (i.e. cases) will be individually validated, and only those found to be valid (either by manual review or related hospital admission from hospital records databases, as proposed above) will be defined as cases.

As for cardiovascular death, HSD, IPCI and SIDIAP will combine ICPC and ICD9/ICD10 codes (for hospital admission/primary care records) respectively with mortality using a time specific window to define cardiovascular death. In THIN, data will be linked to the official mortality registry (office for national statistics) for cause of death. In Aarhus, safety endpoints will be identified in the patient registry (hospital discharge and death registry) and no manual validation in the medical records will be done.

**Control selection:** In the nested case control study, each case will be matched by age (same year of birth), index date, gender, and country/data source to 10 controls selected from the cohort using incidence density sampling.

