#### Exposure categorization for safety studies

For the incidence rate calculations the period of drug use will be divided in mutual exclusive periods of a month to be able to investigate the rate of cardiac events during current, recent or past use. The period 0-180 days after cessation of study drugs use will be classified as recent use and the period 181 days or more will be classified as past use. If patients switch from SR to BP or vice versa, they will contribute to the respective exposure category.

For the case control study we follow the same categorization. A patient will be classified as current user if the last prescription is ongoing or stopped less than 30 days ago before the index date. Patients will be classified as recent users if last prescription stopped between 30 and 180 days before the index date. Patients are past users if the last prescription for a study drug stopped more than 180 days before index date.

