### 9.7.2. Effectiveness of the RMM

#### 9.7.2.1. Utilization of Strontium ranelate

##### *Utilization patterns population level*

*Incidence of SR* use will be calculated by dividing the number of new users in each month of the year by the amount of population person-time in each month. A new user is defined as a person without a prescription for SR in the 365 days prior to the index prescription.

*Prevalence of SR* use will be calculated by dividing the number of patients who have at least one day of SR use in a specific time unit (month or year) by the amount of population person-

time in that time unit (Note person-time is used rather than the number of persons due to the dynamic character of the underlying population).

Prevalence and incidence of SR use in each of the data sources will be calculated with their 95% CIs calculated assuming a binomial and Poisson distribution respectively. All estimates will be stratified by time (month, period and calendar years) as well as by country (database), age and sex and country.

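### Follow-up ends at the database's last data capture, but in IPCI and THIN the data end differs by practice, so unobserved person-time can enter the denominators and control risk sets

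*Protocol*

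**What the plan says.** Both follow-up sections (9.2.6.1 for effectiveness of risk minimization, 9.2.6.2 for safety) stop follow-up at the earlier of two dates. One is "The end of enrolment in the database (due to moving out or death"). The other is the "Date of last data capturing in the database". Section 9.2.2 also sets the end of the study period by source: it "will end at the most recent version of data that is available with each of the database custodians".

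The data-availability table in section 6 gives SIDIAP and the Danish database one end date, 31 December of the previous year, and gives HSD a fixed half-year end. For IPCI and for THIN the entry is "Variable as GPs provide not all at same time".

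Three later rules depend on the end date:

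- Section 9.7.2.1 obtains incidence of SR use by "dividing the number of new users in each month of the year by the amount of population person-time in each month". Prevalence uses the same kind of denominator.
- Section 9.3.3 moves a patient out of current use when prescriptions stop: "The period 0-180 days after cessation of study drugs use will be classified as recent use". Beyond that window the patient counts as a past user.
- Section 9.3.1 matches each case on age, index date, gender and "country/data source to 10 controls selected from the cohort using incidence density sampling". Practice is not a matching factor.

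**The concern.** In IPCI and THIN there is no single date on which data capture stops. A practice that has not yet sent its latest data has neither lost its patients to a move nor to death, so the enrolment rule does not remove them. Under the database-level rule they remain at risk until the cut, with no new GP-recorded prescription or event able to appear.

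Two results are exposed. The first is population-level SR use by period, which is the first effectiveness objective. Blind months add person-time but no users, so use appears to fall in the last months, and those months lie in the assessment period from April 2014. The second is the comparison of current SR with past use of study drugs, the first contrast listed in section 9.7.3.3. Blind time lowers the past-use event rate and supplies controls who could not have become GP-recorded cases.

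**Working it through.** The protocol states no figure for this point, so there is none to reproduce. The steps below establish the reach and then illustrate the size under stated assumptions.

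**1. Reach** (Table (9.5) 1, year 2012)

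- Incident SR users in THIN and IPCI: 514 + 42 = 556; 556 / 5,819 = 9.6%.
- Prevalent SR users: 2,563 + 106 = 2,669; 2,669 / 27,764 = 9.6%.
- Population: 3.5 + 1.2 = 4.7 million; 4.7 / 13.1 = 36%.
- In the planned sensitivity analysis without Spain, the incident share on 2012 counts is 556 / (5,819 - 4,008) = 556 / 1,811 = 30.7%.

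**2. Blind share of person-time in the two sources.** No lag is given. Assume that practices' last uploads are spread evenly over the L months before the database's last date. The mean lag is L/2, so the blind share of the last 12 months is (L/2)/12. In the last month, the share of person-time still visible is 0.5/L.

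| Assumed L (months) | Blind share of last 12 months | Visible share in last month |
|---|---|---|
| 3 | 1.5/12 = 12.5% | 0.5/3 = 17% |
| 6 | 3/12 = 25% | 0.5/6 = 8% |
| 12 | 6/12 = 50% | 0.5/12 = 4% |

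With constant use, incidence in these sources over the last 12 months is understated by the middle column. Prevalence is understated slightly less, because the last visible prescription and its 30-day carry-over run on into the blind time. In a crude rate pooled over all five sources, only 9.6% of new users are exposed to the loss, so the understatement is 0.096 x 25% = 2.4% or 0.096 x 50% = 4.8%.

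**3. Drift into past use.** A patient on treatment at the last upload stays current through the carry-over, then is recent up to 180 days, then past. For lags of at most 180 days the falsely past time is zero. For lags uniform over 0-365 days its mean is (365 - 180)^2 / (2 x 365) = 46.9 days, or (365 - 210)^2 / (2 x 365) = 32.9 days if 30 days of supply remained.

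**4. Past-use rate.** Patients already past at the last upload add blind past-use time at once. If a share g of past-use person-time is blind, the observed rate is (1 - g) times the true rate, and any ratio against it is inflated by 1/(1 - g): 1.05, 1.11 and 1.33 for g = 5%, 10% and 25%.

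**5. Controls.** Let a share f of eligible controls be blind at the index date. Assume that half of the current and past users are truly current and that the true odds ratio is 1.

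- Lags up to 180 days: blind treated controls become at most recent and leave the contrast, while blind past users stay. The odds ratio is at most 0.5 / [0.5(1 - f)] = 1/(1 - f), again 1.05, 1.11 and 1.33.
- Lags beyond 180 days, with all blind controls appearing past: the odds ratio is (0.5 + 0.5f) / [0.5(1 - f)] = (1 + f)/(1 - f), that is 1.11, 1.22 and 1.67.

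The values of f and g are illustrative and cannot be derived from the protocol. They are not the 25% and 50% of step 2, which describe only the last 12 months; safety follow-up reaches back to 2004.

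**6. What cancels.** For current SR versus current bisphosphonate, a lag unrelated to the drug removes the same share (1 - f) of both control groups, so the ratio is unchanged. For proportions among SR users, a blind month loses numerator and denominator together.

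**The case against.** The best defence is that the end date is already meant to be specific to the patient. The matching start rule, one year of valid data, can only be applied patient by patient. Table (9.4) 1 lists an exit date for every database, and section 6 shows that the authors know about staggered uploads. Nothing in the protocol instructs anyone to count time after a practice's last upload, and section 9.7 leaves detail to a statistical analysis plan that is not at hand.

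Part of this stands: counting blind time is the literal reading, not one that the document spells out. It does not settle the point. Ending follow-up at the patient's own last record would be a different rule, and an informative one, because it shortens time for people who do not consult. The protocol does not say how the exit date in Table (9.4) 1 is set, and sections 9.2.6.1 and 9.2.6.2 tie exit only to moving or death. Extraction is local (section 9.6.3), so custodians could apply different end dates under the same sentence.

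The defence is also right that the harm is limited. A reader might infer that the past-use group becomes event-free. It does not: treated patients first pass through recent use, past use before the upload is fully observed, and in THIN the cause of death comes from a linked mortality registry. A reader might also infer a false risk minimization effect in the interrupted time series. Sections 9.7.2.2 and 9.5.1 do not support that, because the series models proportions among SR users; only the descriptive use rates are exposed.

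**Conclusion.** The point holds as a defect in the end-of-follow-up rule. The protocol sets one end date per database and states elsewhere that two of the five databases do not have one. Followed literally, monthly SR use in IPCI and THIN is understated just before each data cut, past-use event rates are diluted, and the odds ratio of current SR versus past use can be biased upward.

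The size rests on practice lags that the protocol does not give. Under uniform lags of 0-6 or 0-12 months, 25% or 50% of the last 12 months of person-time in these sources is blind. Those shares should not be read across to the safety rates, which split at June 2013 by cohort entry and include years of observed time. The reach is two sources with 9.6% of 2012 SR users. Their 36% of the population overstates the weight, because estimates are made per database before pooling. The main safety contrast, current SR versus current bisphosphonate, is largely spared provided that the lag is unrelated to the drug.

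**What to change.** In sections 9.2.6.1 and 9.2.6.2, define the end of follow-up as the earliest of end of enrolment, death, and the last data upload of the patient's practice in IPCI and THIN, or the database's single end date in the other three sources. Apply the same date to population person-time in section 9.7.2.1, to exposure episodes (censor them there and do not let them lapse into recent or past use), and to eligibility as a control at the index date.

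The cost is a short wording change, a practice-level upload date that the custodians should be able to supply, and slightly less person-time in two databases.
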